## **6.2 RESPONSE CRITERIA**

6.2.1 The primary endpoint is median progression-free survival. A combination of the neurological examination and MRI brain scan will be used to define progression. Due to improvements in neuroimaging and the fact that tumor growth in certain regions of the CNS is without immediate neurologic signs and symptoms, greater reliance is placed on neuroimaging to define progression.

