6.2.2 Definitions of Response

6.2.2.1 **Measurable Disease:** Bi-dimensionally measurable lesions with clearly defined margins by MRI scan.

6.2.2.2 **Objective Status, To Be Recorded at Each Evaluation:** If there are too many measurable lesions to measure at each evaluation, choose the largest two to be followed before a patient is entered on study. The remaining lesions will be considered evaluable for the purpose of objective status determination. Unless progression is observed, objective status can only be determined when ALL measurable and evaluable sites and lesions are assessed.

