6.2.3 Response Criteria

6.2.3.1 **Stable/No Progression:** No evidence of new measurable lesions on MR imaging. The designation of Stable/No Progression requires a minimum of 12 weeks duration. All measurable and evaluable sites must be assessed using the same techniques as baseline.

6.2.3.2 **Partial response:**  $\geq 50\%$  reduction in the sum of products of all measurable lesions over baseline sum observed using the same techniques as baseline. The patient must be on a stable or decreased dose of corticosteroids to be evaluable for response.

6.2.3.3 **Complete response:** Complete resolution of all lesions. The patient cannot be on any corticosteroids with the exception of adrenal replacement doses.

6.2.3.4 **Progression:** 25% increase in the sum of products of all measurable lesions over smallest sum observed (over baseline if no decrease) using the same techniques as baseline, OR clear worsening of any evaluable disease, OR appearance of any new lesion/site, OR failure to return for evaluation due to death or deteriorating condition (unless clearly unrelated to this cancer).

6.2.3.5 **Unknown:** Progression has not been documented and one or more measurable or evaluable sites have not been assessed.

6.2.4 **Neurologic Function Score:** This method of neurologic evaluation notes the presence or absence of neurologic symptoms. This examination should coincide with objective measurement in tumor size.

0	No neurologic symptoms
1	Minor neurologic symptoms
2	Moderate neurologic symptoms – fully active
3	Moderate neurologic symptoms – less than fully active
4	Severe neurologic symptoms

- 6.2.5 **Performance Status:** Patients will be graded according to Karnofsky Performance Status (KPS)
- 6.2.6 **Time to Treatment Failure:** From date of registration to the date of first observation of progressive disease, non-reversible neurologic progression or permanently increased steroid requirement (applies to stable disease only), death due to any cause, or early discontinuation of treatment.
- 6.2.7 **Survival:** From date of registration to date of death due to any cause
- 6.2.8 **NOTE: Steroids:** Steroid dosage will be carefully monitored and recorded during each course of therapy and steroid dosage changes will be considered before response determinations are made.

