### Secondary Efficacy Analysis

The secondary endpoint of this trial is anti-tumor activity as determined by the overall response (CR or PR) rate. MacDonald criteria will be used to determine the overall response. Patients must have completed at least 4 weeks of treatment to be considered evaluable for overall response, unless treatment is stopped for neurologic progression. Patients with neurologic progression will be scored as non-responders regardless of duration of treatment.

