#### Neurologic Function

	+2	Definitely Better
	+1	Possibly Better
	0	Unchanged
	-1	Possibly Worse
	-2	Definitely Worse
	B	Baseline

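### Section 6.2.1 makes the neurological examination part of the progression definition, but the operative criterion in 6.2.3.4 has no examination criterion and Section 8 does not settle whether neurologic progression is a primary event

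*Combined protocol and SAP*

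**What the plan says.** Section 6.2.1 names median PFS as the primary endpoint and states: "A combination of the neurological examination and MRI brain scan will be used to define progression". It adds that "greater reliance is placed on neuroimaging to define progression", which weights the two sources but keeps both.

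Section 6.2.3.4 is the definition that sites apply. It is met by 25% growth in the summed lesion products and, failing that, by any one of these: "clear worsening of any evaluable disease, OR appearance of any new lesion/site, OR failure to return for evaluation due to death or deteriorating condition". Decline that plainly has another cause is exempt. Evaluable disease here means lesions: for lesions not chosen for measurement, 6.2.2.2 says "The remaining lesions will be considered evaluable for the purpose of objective status determination".

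Neurologic progression appears by name in two other places. Time to treatment failure (6.2.6) lists progressive disease and then, as a further event, "non-reversible neurologic progression or permanently increased steroid requirement (applies to stable disease only". The Secondary Efficacy Analysis in Section 8 says "Patients with neurologic progression will be scored as non-responders regardless of duration of treatment".

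The opening of Section 8 defines the primary event as progressive disease, toxicity severe enough to prevent continuation, or death. It does not mention neurologic progression.

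**The concern.** The primary endpoint has a stated basis (6.2.1) and an operative rule (6.2.3.4) that classify the same patient differently. The patient at issue still attends visits, has non-reversible neurologic decline, and shows no 25% growth, no worsening of other lesions and no new lesion. The plan expects such patients, since it provides for them in 6.2.6 and in the response analysis.

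Two sites reading different subsections could date this patient's progression differently, or one could record no event at all. Followed literally, 6.2.3.4 waits until imaging catches up, the patient stops returning, or the patient dies. The recorded PFS is then longer than 6.2.1 intends. A single-arm trial has no concurrent control arm in which such a bias could cancel.

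**Working it through.** **1. The passages side by side**

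| Place | Use | Is neurologic progression in an attending patient an event? |
|---|---|---|
| 6.2.1 | Basis for the primary endpoint | Yes on its natural reading; no scale or threshold given |
| 6.2.3.4 | Operative criterion | No; clinical decline counts only through failure to return |
| 6.2.6 | Time to treatment failure | Yes, listed apart from progressive disease |
| Section 8, opening | Primary event | Not named; enters only if it counts as progressive disease |
| Section 8, Secondary Efficacy Analysis | Response | Yes, scored as non-response |

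Because 6.2.6 lists neurologic progression in addition to progressive disease, the plan itself treats it as something that 6.2.3.4 does not already contain. With no new measurable lesion, the same patient could even be labelled stable under 6.2.3.1 once 12 weeks have passed.

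**2. Size of late dating**

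No figure in the plan depends on this point. As a check on the Section 8 model, its credible limits reproduce closely: 8.78-12.63 against the stated 8.72-12.50 for a true median of 10.5 months, and 11.51-16.70 against 11.52-16.66 for 14 months.

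Inputs:
- Exponential PFS (Section 8), so the median estimate is ln 2 × total time / events.
- Share q of progressions that are clinical first: not in the documents; assumed 10-20%.
- Delay d until a qualifying event: not in the documents; assumed 2-4 months. MRI and neurologic examination are both every 8 weeks on treatment (3.7.1, 3.7.3), and 56/30.44 = 1.84 months, so this is about one to two scans.

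Delaying a share q of the events by d adds q × d per event to total time and leaves the event count unchanged. The median therefore rises by ln 2 × q × d:
- Low end: 0.693 × 0.10 × 2 = 0.14 months.
- High end: 0.693 × 0.20 × 4 = 0.55 months.

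The Section 8 prior hardly changes this. With 50 events the shift in the posterior mean is multiplied by 50/51.

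**3. Check by simulation on the 8-week grid**

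The assumed share was widened to 10-50%, with a true median of 10.5 or 14 months. Dating clinical-first events at the next scan instead of at onset raises the estimate by 0.06-0.32 months. One further scan of delay makes the total 0.19-0.96 months.

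For a 20% share, a true median of 10.5 months and the stopping rule as printed, the probability of stopping early falls from 0.34 (dated at onset) to 0.27 (next scan) and 0.21 (one scan later). These three values show direction only. Without scan-based dating, simulating the printed rule at this median gives 0.56-0.78 depending on accrual and follow-up settings, against the plan's 0.173.

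**The case against.** The other side has four fair arguments.

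- **Clinical decline is not wholly absent.** A reader might infer that 6.2.3.4 leaves clinical progression out altogether. It does not: deterioration that prevents return counts. The gap is the patient who still attends, plus the lack of a dating rule for those who do not.
- **The emphasis on imaging is deliberate.** Section 6.2.1 gives reasons for it. That explains a lower weight for the examination, but not a criterion in which it has no weight. The word for combining the two could be read as requiring both together; on that reading too, 6.2.3.4 lacks the examination.
- **The effect on the historical comparison is unknown.** Section 1.2.2 reports a median time to progression of 9.9 months and Section 8 uses 10.5 months, neither with a definition of progression. If the benchmark was imaging-based, adding neurologic events could create a mismatch. This stands: the upward bias is relative to the plan's own 6.2.1 definition, and its effect on the comparison with history cannot be determined.
- **Accrual is closed (2.3).** Redefining the event now invites the charge of a post hoc change. This also stands, and it bears on how the fix is documented.

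Two further inferences are tempting and unsupported. The first is that clinical-first patients are censored without an event, which would inflate a 10.5-month median to 10.5/0.9 = 11.7 or 10.5/0.8 = 13.1 months. The documents state no such censoring rule. Section 3.7.9 continues MRI for stable or responding patients, and quarterly disease and survival updates for those removed for progression or toxicity. The latter have no scheduled MRI, so missed events are possible, but their number cannot be derived.

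The second is that the two neurologic scales cause the gap. The 6.2.4 score runs from 0 to 4, where 4 is "Severe neurologic symptoms", and records current status. The Appendix 12.1 score runs from +2 to -2, where -2 is "Definitely Worse", and records change from baseline. Neither feeds 6.2.3.4.

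**Conclusion.** The contradiction is real and concerns the primary endpoint. Sections 6.2.1 and 6.2.3.4 disagree on one identifiable kind of patient, 6.2.6 and the response analysis count that patient's event, and the primary event in Section 8 leaves it open. Literal use of 6.2.3.4 biases median PFS upward.

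The size is modest under the stated assumptions: about 0.14-0.55 months from late dating, against an offset of 3.5 months. The share and the delay are both assumed. Events missed altogether would add to this by an amount the documents do not allow one to calculate. The point should be fixed, but late dating of this size would not by itself span the design's margin.

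The near-identical names and opposite directions of the two neurologic scales are a separate, minor labelling risk.

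**What to change.** Reconcile 6.2.1, 6.2.3.4, 6.2.6 and the opening of Section 8 into one event definition for the primary analysis:

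- In line with 6.2.1, count non-reversible neurologic progression as worded in 6.2.6, dated at the examination that first shows it. State whether the stable-disease qualifier in 6.2.6 covers this event or only the steroid item.
- State which neurologic measure and threshold apply. The documents give no basis for a particular cut-off, so the sponsor should choose and justify it.
- Give a date rule for failure to return because of deterioration.
- State how the toxicity event in Section 8 is handled, since neither 6.2.1 nor 6.2.3.4 includes it.
- Report imaging-only PFS, using 6.2.3.4 as written, as a sensitivity analysis.

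Progression is also a reason for removal from therapy (3.8.1.1). Those passages must be reconciled separately; this point concerns the analysis definition only.

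As a minor addition, label the 6.2.4 and Appendix 12.1 scores distinctly and print the direction of each.

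The cost is protocol and analysis wording, form labels and possibly a re-review of event dates. On treatment, examinations are already scheduled at the MRI visits. PFS may come out slightly shorter, and some judgement enters the clinically dated events. Because accrual is closed, the clarification should be documented before the analysis.

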### **6.3 TOXICITY CRITERIA**

The following adverse event management guidelines are intended to ensure the safety of each patient while on the study. The descriptions and grading scales found in the revised NCI Common Terminology Criteria for Adverse Events (CTCAE) version 4.0 will be utilized for AE reporting. All appropriate treatment areas should have access to a copy of the CTCAE version 4.0. A copy of the CTCAE version 4.0 can be downloaded from the CTEP web site ([http://ctep.cancer.gov/protocolDevelopment/electronic\\_applications/ctc.htm#ctc\\_40](http://ctep.cancer.gov/protocolDevelopment/electronic_applications/ctc.htm#ctc_40)).

## **7 SAFETY REPORTING REQUIREMENTS/DATA AND SAFETY MONITORING PLAN**

### **7.1 PROTOCOL SPECIFIC DEFINITIONS**

- 7.1.1 Events *not* considered to be serious adverse events are hospitalizations for the purposes of this protocol and include:
  - Routine treatment or monitoring of the studied indication not associated with any deterioration in condition.
  - treatment, which was elective or pre-planned, for a pre-existing condition that did not worsen
  - treatment on an emergency, outpatient basis for an event *not* fulfilling any of the definitions of serious given above and *not* resulting in hospital admission.
  - Pregnancy, although not itself a serious adverse event, should also be reported on a serious adverse event form and be followed up to determine outcome, including spontaneous or voluntary termination, details of birth, and the presence or absence of any birth defects or congenital abnormalities.
  - Liver function abnormalities meeting pre-defined stopping criteria (See section 3.7.6 & Appendix 12.5) will be reported promptly to NCI once the investigator determines that the event meets the protocol definition for that event
- 7.1.2 In addition to reporting the SAEs described below, the following protocol specific reporting criteria will be reported:
  - All Grade 4 laboratory abnormalities.

- Cardiovascular events have been seen in subjects taking other compounds that inhibit ErbB2 when used in combination with or following anthracyclines and interstitial pneumonitis has been reported in subjects taking compounds that inhibit ErbB1. As a precaution, the following will be reported as SAE:
  - Cardiac dysfunction will be reported as an SAE and will be defined as any signs or symptoms of deterioration in left ventricular cardiac function that are  $\geq$ Grade 3 (NCI CTCAE) or a  $\geq$ 20% decrease in LVEF relative to baseline, which is also, below the institution's LLN. Refer to NCI CTCAE grading of left ventricular cardiac function.
  - Any signs or symptoms of pneumonitis that are  $\geq$ Grade 3 (NCI CTCAE) (defined as radiographic changes and requiring oxygen). Refer to NCI CTCAE grading of pneumonitis/pulmonary infiltrates.
  - Hepatobiliary events have been seen in subjects taking lapatinib and other tyrosine kinase inhibitors. As a precaution, the following will be reported as an SAE:
    - ALT  $>3 \times$  ULN and total bilirubin  $>2.0 \times$  ULN ( $>35\%$  direct; bilirubin fractionation required).
    - **NOTE:** bilirubin fractionation should be performed if testing is available. If testing is unavailable and a subject meets the criterion of total bilirubin  $>2.0 \times$  ULN, then the event should still be reported as an SAE. Other hepatic events should be documented as an AE or an SAE as appropriate.

## **7.2 GENERAL DEFINITIONS**

### **7.2.1 Adverse Event**

An adverse event is defined as any reaction, side effect, or untoward event that occurs during the course of the clinical trial associated with the use of a drug in humans, whether or not the event is considered related to the treatment or clinically significant. For this study, AEs will include events reported by the patient, as well as clinically significant abnormal findings on physical examination or laboratory evaluation. A new illness, symptom, sign or clinically significant laboratory abnormality or worsening of a pre-existing condition or abnormality is considered an AE. All AEs must be recorded on the AE case report form.

All AEs, including clinically significant abnormal findings on laboratory evaluations, regardless of severity, will be followed until return to baseline or stabilization of event. Serious adverse events that occur more than 30 days after the last administration of investigational agent/intervention and have an attribution of at least possibly related to the agent/intervention should be recorded and reported as per section 7.4

An abnormal laboratory value will be considered an AE if the laboratory abnormality is characterized by any of the following:

- Results in discontinuation from the study
- Is associated with clinical signs or symptoms
- Requires treatment or any other therapeutic intervention

- Is associated with death or another serious adverse event, including hospitalization.
- Is judged by the Investigator to be of significant clinical impact
- If any abnormal laboratory result is considered clinically significant, the investigator will provide details about the action taken with respect to the test drug and about the patient's outcome.

#### 7.2.2 Suspected adverse reaction

Suspected adverse reaction means any adverse event for which there is a reasonable possibility that the drug caused the adverse event. For the purposes of IND safety reporting, 'reasonable possibility' means there is evidence to suggest a causal relationship between the drug and the adverse event. A suspected adverse reaction implies a lesser degree of certainty about causality than adverse reaction, which means any adverse event caused by a drug.

#### 7.2.3 Unexpected adverse reaction

An adverse event or suspected adverse reaction is considered "unexpected" if it is not listed in the investigator brochure or is not listed at the specificity or severity that has been observed; or, if an investigator brochure is not required or available, is not consistent with the risk information described in the general investigational plan or elsewhere in the current application. "Unexpected" also refers to adverse events or suspected adverse reactions that are mentioned in the investigator brochure as occurring with a class of drugs or as anticipated from the pharmacological properties of the drug, but are not specifically mentioned as occurring with the particular drug under investigation.

#### 7.2.4 Serious

An Unanticipated Problem or Protocol Deviation is serious if it meets the definition of a Serious Adverse Event or if it compromises the safety, welfare or rights of subjects or others.

#### 7.2.5 Serious Adverse Event

An adverse event or suspected adverse reaction is considered serious if in the view of the investigator or the sponsor, it results in any of the following:

- Death,
- A life-threatening adverse drug experience
- Inpatient hospitalization or prolongation of existing hospitalization
- Persistent or significant incapacity or substantial disruption of the ability to conduct normal life functions
- A congenital anomaly/birth defect.
- Important medical events that may not result in death, be life-threatening, or require hospitalization may be considered a serious adverse drug experience when, based upon appropriate medical judgment, they may jeopardize the patient or subject and may require medical or surgical intervention to prevent one of the outcomes listed in this definition.

#### 7.2.6 Disability

A substantial disruption of a person's ability to conduct normal life functions.

#### 7.2.7 Life-threatening adverse drug experience

Any adverse event or suspected adverse reaction that places the patient or subject, in the view of the investigator or sponsor, at immediate risk of death from the reaction as it occurred, i.e., it does not include a reaction that had it occurred in a more severe form, might have caused death.

#### 7.2.8 Protocol Deviation (NIH Definition)

Any change, divergence, or departure from the IRB-approved research protocol.

#### 7.2.9 Non-compliance (NIH Definition)

The failure to comply with applicable NIH Human Research Protections Program (HRPP) policies, IRB requirements, or regulatory requirements for the protection of human research subjects.

#### 7.2.10 Unanticipated Problem

Any incident, experience, or outcome that:

- Is unexpected in terms of nature, severity, or frequency in relation to
  - (a) the research risks that are described in the IRB-approved research protocol and informed consent document; Investigator's Brochure or other study documents, and
  - (b) the characteristics of the subject population being studied; **AND**
- Is related or possibly related to participation in the research; **AND**
- Suggests that the research places subjects or others at a *greater risk of harm* (including physical, psychological, economic, or social harm) than was previously known or recognized.

### 7.3 ASSESSING CAUSALITY

Investigators are required to assess whether there is a reasonable possibility that the study agent/s caused or contributed to an adverse event. The following general guidance may be used.

*Yes:* If the temporal relationship of the clinical event to the study agent/s administration makes a causal relationship possible, and other drugs, therapeutic interventions or underlying conditions do not provide a sufficient explanation for the observed event.

*No:* If the temporal relationship of the clinical event to the study agent/s administration makes a causal relationship unlikely, or other drugs, therapeutic interventions or underlying conditions provide a sufficient explanation for the observed event.

### 7.4 NCI-IRB AND CLINICAL DIRECTOR REPORTING

#### 7.4.1 NCI-IRB and NCI CD Expedited Reporting of Unanticipated Problems and Deaths

The Protocol PI will report in the NIH Problem Form to the NIH-IRB and NCI Clinical Director:

- All deaths, except deaths due to progressive disease
- All Protocol Deviations

- All Unanticipated Problems
- All non-compliance

Reports must be received within 7 days of PI awareness via iRIS.

#### 7.4.2 NCI-IRB Requirements for PI Reporting at Continuing Review

The protocol PI will report to the NCI-IRB:

1. A summary of all protocol deviations in a tabular format to include the date the deviation occurred, a brief description of the deviation and any corrective action.
2. A summary of any instances of non-compliance
3. A tabular summary of the following adverse events:
  - All Grade 2 **unexpected** events that are possibly, probably or definitely related to the research;
  - All Grade 3 and 4 events that are possibly, probably or definitely related to the research;
  - All Grade 5 events regardless of attribution;
  - All Serious Events regardless of attribution.

**NOTE:** Grade 1 events are not required to be reported.

